3.4.3.3 CC-486 (5-azacitidine)

CC-486 (5-azacitidine) will be administered on days 1 through 10 of each cycle in the clinic. CC-486 (5-azacitidine) will be taken orally, with or without food. The tablets/ capsules must be swallowed whole and may be taken with or without food.

3.4.3.4 Dexamethasone

Dexamethasone will be administered orally on Days 1 and 10.

3.4.3.5 Study Drug Diaries

Patients will be required to complete and return a drug diary as a memory aid to help document the date and time of all self-administered study drugs ([Appendix F](#)). This drug diary as well as study drug containers and any unused study drug should be returned to the research team at the end of each cycle of therapy.

3.4.4 Supportive Medications

3.4.4.1 Prophylactic and supportive care for lenalidomide

Patients who are not already on prophylactic or therapeutic doses of anticoagulants will be given aspirin 81mg by oral intake for prophylaxis of venous thromboembolism.

3.4.4.2 Prophylactic and supportive care for romidepsin and CC-486 (5-azacitidine)

Patients will be given ondansetron 16 mg orally or 8 mg IV (or equivalent dose of granisetron orally or transdermal in case of allergy or intolerance to ondansetron) to prevent chemotherapy-associated nausea. Anti-emetics may be omitted during the second and subsequent cycles at investigators' discretion.

3.4.4.3 Other modalities or procedures

- Patients deemed by the PI or treating investigator to be at high risk for CNS relapse who have not received CNS prophylaxis as part of their prior treatment may receive prophylaxis in the form of cytarabine 40 mg, methotrexate 15 mg, and hydrocortisone 50 mg administered intrathecally (IT) no earlier than Day 2 of Cycle 1 and every 3-6 weeks thereafter for up to six doses. Cytarabine or methotrexate may be omitted in case of prior intolerance or toxicity attributed to either drug. Platelet counts of $\geq 70,000$ / μ L need to be confirmed prior to each administration.
- If CNS disease is detected at screening or during prophylactic IT drug administration, IT treatment listed above will be administered twice weekly until abnormal lymphoid cells are no longer detectable by cytology or flow cytometry, then weekly for four additional doses.
- Patients with bulky disease (one or more lymph nodes ≥ 10 cm), high leukemic cell count ($\geq 50,000$ cells/ mm^3) or who are for other reasons deemed by the PI or designate to be at an increased risk for tumor lysis syndrome will have the laboratory evaluations as listed in Study Calendar (Section [3.9](#)).
- Patients will be observed in the day hospital or the inpatient unit for at least 30 minutes after administration of romidepsin for potential infusion-related reactions.

3.4.5 Missed doses

All missed doses of the protocol medications administered orally (CC-486 (5-azacitidine), lenalidomide, and dexamethasone) will be recorded in the primary source documentation at the time of the next patient visit. If a dose is not taken at the scheduled time and it has been less than 12 hours since the regularly scheduled time, it can be taken as soon as possible on the same day. If it has been more than 12 hours, the missed dose may be skipped, but the next dose should be taken at the normal time on the following day. The patient should not take extra doses to make up the missed dose.

If the patient has an episode of emesis and vomits a dose of one or more drugs, these will be recorded as missed and will not be re-administered. If there is only suspicion that the doses were vomited because emesis occurred, but there is no clear evidence for it, these doses will not be recorded as missed.

3.5 DOSE MODIFICATION

Previous clinical trial experience treating patients with relapsed refractory TCMs indicates significant efficacy for the 2 drug combinations of romidepsin and oral 5-azacitidine [63] or romidepsin and Lenalidomide [58], but the AE listings shown below in **Table 5** also illustrate the potential for overlapping toxicity that may make it difficult to attribute specific AEs to only one of the investigational agents as well as highlight the potential for more significant AEs with the addition of the 3rd active agent. While patient safety is always of foremost concern, there will be interest in maintaining dose intensity and continuing treatment to accurately assess the clinical activity of this regimen. The single agent safety experience will provide important insight into each drugs contribution to the hematologic and GI toxicities, but individual AEs may require interrupting treatment, dose reduction or discontinuation of more than 1 drug.

Table 5: Adverse Event listings for Romidepsin/5-azacitidine Treatment emergent AEs occurring in 10% or more of the patients (n = 25)

AE	Total	Grade 1-2	Grade 3-4
Decreased platelet count	18 (72)	6 (24)	12 (48)
Decreased neutrophil count	17 (68)	7 (28)	10 (40)
Nausea	17 (68)	15 (60)	2 (8)
Hyperglycemia	15 (60)	14 (56)	1 (4)
Anemia	14 (56)	10 (40)	4 (16)
Fatigue	14 (56)	13 (52)	1 (4)
Decreased lymphocyte count	13 (52)	5 (20)	8 (32)
Diarrhea	12 (48)	12 (48)	—
Constipation	12 (48)	12 (48)	—
Vomiting	12 (48)	10 (40)	2 (8)

AE	Total	Grade 1-2	Grade 3-4
Hypoalbuminemia	11 (44)	11 (44)	—
Anorexia	10 (40)	10 (40)	—
Increased creatinine	10 (40)	10 (40)	—
Fever	8 (32)	7 (28)	1 (4)
Abdominal pain	7 (28)	6 (24)	1 (4)
Upper respiratory infection	7 (28)	6 (24)	1 (4)
Hypocalcemia	7 (28)	7 (28)	—
Headache	6 (24)	6 (24)	—
Weight loss	6 (24)	6 (24)	—
Hypophosphatemia	6 (24)	4 (16)	2 (8)
Hyponatremia	5 (20)	5 (20)	—
Dysgeusia	5 (20)	5 (20)	—
Increased aspartate aminotransferase	5 (20)	5 (20)	1 (4)
Hypokalemia	5 (20)	5 (20)	—
Rash maculopapular	4 (16)	4 (16)	—
Increased blood bilirubin	4 (16)	2 (8)	2 (8)
Urinary tract infection	4 (16)	3 (12)	1 (4)
Cough	4 (16)	4 (16)	—
Chronic kidney disease	4 (16)	4 (16)	—
Malaise	3 (12)	3 (12)	—
Nasal congestion	3 (12)	3 (12)	—
Hypoglycemia	3 (12)	3 (12)	—
Hypercalcemia	3 (12)	3 (12)	—
Increased alanine aminotransferase	3 (12)	2 (8)	1 (4)
Hypernatremia	3 (12)	3 (12)	—
Myalgia	3 (12)	3 (12)	—
Peripheral sensory neuropathy	3 (12)	3 (12)	—
Edema in the limbs	3 (12)	3 (12)	—

AE	Total	Grade 1-2	Grade 3-4
Dizziness	3 (12)	3 (12)	—
Arthralgia	3 (12)	3 (12)	—
Febrile neutropenia	3 (12)	—	3 (12)
Dyspepsia	3 (12)	3 (12)	—
Back pain	3 (12)	3 (12)	—

Table 5.1 Toxicities occurring in $\geq 10\%$ of participants and all grade three and grade four toxicities for Regimen A (romidepsin and lenalidomide)

	Regimen A					
	Any grade occurring in $\geq 10\%$ n (%)		Grade 3		Grade 4	
Hematological toxicities	43	88%	24	49%	18	37%
Anemia	16	33%	13	27%	—	—
Febrile neutropenia	—	—	3	6%	—	—
Neutropenia	28	57%	15	31%	9	18%
Thrombocytopenia	30	61%	18	37%	8	16%
Lymphocyte count decreased	28	57%	16	33%	9	18%
White blood cell decreased	22	45%	18	37%	4	8%
Liver function toxicities	9	18%	2	4%	—	—
Alanine aminotransferase increased	—	—	—	—	—	—
Aspartate aminotransferase increased	—	—	—	—	—	—
Alkaline phosphatase increased	—	—	1	2%	—	—
Blood bilirubin increased	5	10%	1	2%	—	—
Hypoalbuminemia	—	—	—	—	—	—
Electrolyte toxicities	27	55%	24	49%	—	—
Hyperglycemia	8	16%	7	14%	—	—
Hypermagnesemia	10	20%	10	20%	—	—

	Regimen A				
	Any grade occurring in $\geq 10\%$ n (%)		Grade 3	Grade 4	
Hypocalcemia	5	10%	5	10%	—
Hypoglycemia	—	—	—	—	—
Hypokalemia	6	12%	6	12%	—
Hypomagnesemia	—	—	—	—	—
Hyponatremia	—	—	1	2%	—
Hypophosphatemia	8	16%	8	16%	—
Creatinine increased	—	—	—	—	—
Other toxicities	48	98%	20	41%	—
Abdominal pain	6	12%	—	—	—
Anorexia	18	35%	1	2%	—
Arthralgia	—	—	1	2%	—
Chills	—	—	—	—	—
Constipation	19	39%	—	—	—
Dehydration			3	6%	—
Diarrhea	19	39%	—	—	—
Dysgeusia	30	61%	—	—	—
Dyspnea	5	10%	1	2%	—
Electrocardiogram QT corrected interval prolonged	—	—	1	2%	—
Fatigue	31	63%	11	22%	—
Fever	5	10%	—	—	—
Generalized muscle weakness	—	—	1	2%	—
Headache	—	—	—	—	—
Hypotension	—	—	—	—	—
Lung infection			3	6%	—

	Regimen A					
	Any grade occurring in $\geq 10\%$ n (%)		Grade 3		Grade 4	
Malaise	—	—	—	—	—	—
Myalgias	7	14%	—	—	—	—
Nausea	30	63%	—	—	—	—
Phlebitis	—	—	—	—	—	—
Rash Maculo-Papular	—	—	1	2%	—	—
Syncope	—	—	1	2%	—	—
Tumor lysis syndrome	—	—	1	2%	—	—
Upper respiratory infection	—	—	1	2%	—	—
Vomiting	15	27%	—	—	—	—
Weight loss	12	22%	—	—	—	—

3.5.1 Treatment modifications for adverse reactions

All treatment modifications should be discussed with the senior clinical investigators on the study. Treatment modifications will follow the guidelines outlined in [Table 6](#). Any given dose modification after Cycle 1 can be repeated twice in a patient as long as the patient is benefiting from therapy and does not meet off-treatment criteria.

If a toxicity which requires modification of therapy per [Table 6](#) occurs during the window period (day -7 to day -1) and does not meet the definition of a DLT, cycle 1 day 1 may start after resolution to grade ≤ 1 (grade ≤ 2 for anemia).

All grading scales in the following tables are according to the revised NCI Common Terminology Criteria for Adverse Events (CTCAE) version 5.0.

Table 6: Dose Modification of Lenalidomide, romidepsin and CC-486 (5-azacitidine) for treatment related AEs

Event	Initial management	Follow-up Management
Cycle 1 DLT Evaluation Period		
Grade 1 AEs		
Any AE	Continue treatment	Continue monitoring and laboratories at least once weekly
Grade 2 AEs		
ANC: $<1.5 - 1.0 \times 10^9/L$	Continue treatment	Monitor cell counts at least twice weekly Pegfilgrastim*

Event	Initial management	Follow-up Management
Platelet: < 75,000 - 50,000/mcL	Consider holding treatment for up to 7 days	Monitor cell counts at least twice weekly Restart treatment when platelet count >75,000/mcL
Hgb: < 10.0 - 8.0g/dL	Continue treatment	Monitor cell counts at least twice weekly Consider transfusion before cycle 2
Any other AE	Continue treatment	Continue monitoring and laboratories once weekly
Grade 3 AEs		
ANC: <1.0 -0.5 x 10⁹/L	Hold treatment for up to 7 days Restart treatment at full doses	Monitor cell counts at least twice weekly G-CSF# and Pegfilgrastim*;
Platelet: <50,000 - 25,000/mcL	Hold treatment for up to 7 days Restart treatment at when platelets > 75,000/mcL	Monitor cell counts at least twice weekly If platelets are not > 75,000/mcL the patient is off treatment DLT
Hgb < 8.0g/dL	Hold treatment for up to 7 days Restart treatment after transfusion	Monitor cell counts at least twice weekly Transfusion until Hgb > 9 g/L
Any other AE	Hold treatment for up to 7 days Restart treatment when AE has resolved to ≤ grade 1	Continue monitoring and laboratories at least twice weekly If the AE has not improved to ≤ grade 1, the patient is off treatment DLT
Grade 4 AEs at any time during cycle 1		
Any AE	Discontinue treatment	Off treatment DLT
Cycles 2 through 6		
Event	Initial management	Follow-up Management
Grade 1 AEs		
Any AE	Continue treatment	Continue monitoring and laboratories at least once weekly
Grade 2 AEs		
ANC: <1.5 – 1.0 x 10⁹/L	Continue treatment	Monitor cell counts at least twice weekly
Platelets <75,000 to 50,000/mcL	Continue treatment	Monitor cell counts at least twice weekly
Hgb: < 10.0 – 8.0g/dL	Continue treatment	Consider transfusion before the start of next cycle
Any other AE	Continue treatment	Continue monitoring and laboratories at least twice weekly

Event	Initial management	Follow-up Management
Grade 3 AEs		
ANC: < 1.0 - 0.5 x 10 ⁹ /L Or	1st event: continue treatment	Monitor cell counts at least twice weekly and use G-CSF support for the remainder of current cycle and all future cycles
	2nd event: hold lenalidomide and 5-azacytidine for remainder of cycle; next cycle may resume once ANC is >1.0	Monitor cell counts at least twice weekly and use G-CSF support Dose reduce both 5-azacytidine and lenalidomide for the next cycle
	3rd event: hold lenalidomide and 5-azacytidine for remainder of cycle; next cycle may resume once ANC is >1.0	Monitor cell counts at least twice weekly and use G-CSF support 2nd dose reduction of 5-azacytidine and lenalidomide and consider dose reduction of romidepsin with the next cycle
	4th event: hold lenalidomide and 5-azacytidine for remainder of cycle	Off study treatment
Platelet: <50,000 - 25,000/mcL	1st event: hold lenalidomide and 5-azacytidine for remainder of cycle; next cycle may resume once platelets are >75,000/mcL	Dose reduce both 5-azacytidine and lenalidomide for the next cycle
	2nd event: hold lenalidomide and 5-azacytidine for remainder of cycle; next cycle may resume once platelets are >75,000/mcL	2nd dose reduction of both 5-azacytidine and lenalidomide for the next cycle; consider dose reduction of romidepsin
	3rd event: hold lenalidomide and 5-azacytidine for remainder of cycle	Off study treatment
Hgb < 8.0g/dL	Continue treatment and consider blood transfusion	Monitor cell counts at least twice weekly
Any other grade 3 AE at least possibly related to study treatment	1st event: hold study treatment for the remainder of the cycle	Continue monitoring and laboratories at least twice weekly 1st Dose reduction of 5-azacytidine and lenalidomide for the next cycle
	2nd event: hold treatment for the remainder of the cycle	2nd dose reduction of 5-azacytidine and lenalidomide and consider 1st dose reduction of romidepsin
	3rd event: hold study treatment for the remainder of the cycle	Off study treatment
Grade 4 AEs		
ANC < 0.5 x 10 ⁹ /L or Platelets <25,000/mcL	1st event: hold study treatment for the remainder of the cycle; next cycle may resume once ANC is >1.0 and platelets are >75,000/mcL	Monitor cell counts at least twice weekly Dose reduce 5-azacytidine and lenalidomide next cycle Consider dose reduction of romidepsin

Event	Initial management	Follow-up Management
	2nd event: hold study treatment for the remainder of the cycle	Monitor cell counts at least twice weekly 2nd dose reduction of 5-azacytidine, lenalidomide with next cycle, 1st dose reduction of romidepsin
Hgb Life threatening	Discontinue treatment	Off treatment unacceptable toxicity
Any other AE	1st event: hold treatment 7 to 14 days 2nd event: discontinue treatment	Continue monitoring and laboratories at least twice weekly 1 to 2 dose level reduction of 5-azacytidine or lenalidomide or romidepsin for most likely causative agent or all 3 drugs Consider discontinuation of treatment Off treatment unacceptable toxicity

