3.2 DOSE LIMITING TOXICITY

A dose-limiting toxicity (DLT) is defined as: any treatment-emergent and related severe (grade \geq 3) toxicity, i.e., toxicity deemed related to lenalidomide, romidepsin and/or CC-486 (5-azacitidine) by the PI or designee and occurring during the MTD observation time, defined as day -7 until end of cycle 1 (normally day 22). Each patient must receive all doses of the investigational medications during cycle 1 to be considered as successfully completing the DLT evaluation period.

The following toxicities and conditions will be recorded, however they will not be considered to be DLTs:

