3.2.1 Hematologic exceptions

- Grade 3 or 4 lymphocytopenia without clinical signs of infection grade 2 or above.
 - Lenalidomide, romidepsin and CC-486 (5-azacitidine) will be continued in the event of asymptomatic grade 3 or 4 lymphocytopenia, unless there are clinical signs of significant infection (persistent fevers, labile blood pressure, localized complaints or findings on physical examination, hypoxia or organ dysfunction).
- Grade 3 neutropenia without clinical signs of infection grade 2 or above.
 - Lenalidomide, romidepsin and CC-486 (5-azacitidine) will be continued in the event of grade 3 neutropenia unless there are clinical signs of significant infection, as listed above.
- Grade 3 thrombocytopenia without signs of bleeding that resolved within 7 days of holding the study drug(s) (See Section 3.5.1 for study drug holding parameters).
- Grade 3 anemia that improves to Grade ≤ 2 after transfusion of up to two units of pRBCs and does not recur within 7 days.
- Grade 3 febrile neutropenia (grade 3 febrile neutropenia at any time during therapy will be considered an SAE but not DLT)

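### In cycle 1, Table 6 holds or stops treatment, or records a DLT, for some events that Section 3.2 exempts, chiefly uninfected lymphocytopenia and grade 3 rash that settles only to grade 2

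*Combined protocol and SAP*

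**What the plan says.** Section 3.2 opens with a definition: "A dose-limiting toxicity (DLT) is defined as: any treatment-emergent and related severe" toxicity of grade 3 or higher, within the observation window. It then lists exceptions: "The following toxicities and conditions will be recorded, however they will not be considered to be DLTs". Those that matter here are:

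- Lymphocytopenia (3.2.1): "Grade 3 or 4 lymphocytopenia without clinical signs of infection grade 2 or above". The three drugs "will be continued in the event of asymptomatic grade 3 or 4 lymphocytopenia", again unless there is significant infection.
- Neutropenia (3.2.1): uninfected grade 3 is exempt, and the drugs "will be continued in the event of grade 3 neutropenia unless there are clinical signs of significant infection".
- Febrile neutropenia (3.2.1): "grade 3 febrile neutropenia at any time during therapy will be considered an SAE but not DLT". No recovery condition is attached.
- Rash (3.2.2): grade 3 is exempt if it falls to grade 2 or lower within seven days of a hold.
- Electrolytes and albumin (3.2.2): listed grade 3 abnormalities that last under 72 hours and respond to treatment are exempt, and the drugs continue meanwhile.

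The cycle-1 block of Table 6 has grade 3 rows for ANC, platelets, hemoglobin and a catch-all for any other event. The catch-all row orders a hold of at most seven days and a restart at grade 1 or lower; otherwise the patient goes off treatment with a DLT. Under "Grade 4 AEs at any time during cycle 1" there is one row for all events: discontinue, off treatment, DLT. It has no exception. No sentence says which section prevails.

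**The concern.** An investigator with a cycle-1 patient who has grade 4 lymphocytopenia and no infection finds two written instructions. One continues all drugs and counts no DLT; the other stops them and counts one.

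Two things are at stake. First, the MTD is a primary endpoint and rests on DLT counts. In a 3+3 design one reclassified patient moves 0/3 to 1/3, which calls for expansion instead of escalation, or 1/6 to 2/6, which ends escalation. Second, evaluability depends on the same reading. Section 3.2 requires that "Each patient must receive all doses of the investigational medications during cycle 1 to be considered as successfully completing the DLT evaluation period", and Section 10.3.4 replaces anyone who neither had a DLT nor finished cycle 1. A patient stopped under Table 6 but classified under Section 3.2 therefore leaves the DLT denominator because of an event the protocol calls acceptable.

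**Working it through.** **Text comparison (treatment-related events in cycle 1)**

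| Event | Section 3.2 | Table 6, cycle 1 | Result |
|---|---|---|---|
| Grade 4 lymphocytopenia, uninfected | Not a DLT; continue | Discontinue; DLT | Firm conflict on status and order |
| Grade 3 lymphocytopenia, uninfected | Not a DLT; continue | Catch-all row: hold; DLT only if still above grade 1 after the hold | Firm conflict on order always, on status when unresolved |
| Grade 3 rash at grade 2, not grade 1, within seven days | Not a DLT | Catch-all row: DLT | Firm conflict on status |
| Grade 3 febrile neutropenia, unresolved after the hold | Not a DLT | DLT if read under the catch-all row; no DLT label if read under the ANC row | Softer |
| Grade 3 neutropenia, uninfected | Not a DLT; continue | ANC row: hold, then full doses; no DLT label | Conflict on order only |
| Transient grade 3 electrolyte event | Not a DLT; continue | Catch-all row: hold | Conflict on order |

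**The plan's own figure.** For a true DLT rate p, P(escalate) = (1−p)³ + 3p(1−p)²(1−p)³. At p = 0.10 this is 0.729 + 3 × 0.10 × 0.81 × 0.729 = 0.906. For p = 0.10 to 0.60 in steps of 0.10 it gives 0.906, 0.709, 0.494, 0.309, 0.172 and 0.082, which reproduces the Section 10.2 table.

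**What reclassification could do (assumed rates).** Let other DLTs occur in 10% of patients, and let q be the share whose only DLT-type event is one that Table 6 adds. Then p = 0.10 + q:

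- q = 0, 0.02, 0.05, 0.10 gives P(escalate) = 0.906, 0.871, 0.814, 0.709.
- If the two kinds of event are instead independent, p = 1 − 0.90(1−q), and q = 0.05 and 0.10 give 0.824 and 0.730.
- At a level with 1/6 DLTs, the chance that at least one of the other five is reclassified is 1 − (1−q)⁵ = 0, 0.096, 0.226, 0.410 for the same four values of q.

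**How common the event may be.** The documents give no cycle-1 rates for this regimen. For romidepsin with 5-azacitidine, grade 3-4 lymphopenia is 39% in Section 1.7 and 8/25 = 32% in Table 5. For romidepsin with lenalidomide, Table 5.1 gives grade 3 in 16 patients (33%) and grade 4 in 9 (18%). These come from two-drug regimens on other schedules, are not shown as cycle-1 rates, and are not limited to uninfected patients.

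**Arm 3.** Let r be the assumed share with uninfected grade 3-4 lymphocytopenia in cycle 1. The chance that at least one of n patients meets contradictory orders is 1 − (1−r)ⁿ. Section 2.5.1 allows up to 6 additional patients; Section 10.2 says 3 to 6.

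| r | n = 3 | n = 6 |
|---|---|---|
| 0.05 | 0.143 | 0.265 |
| 0.10 | 0.271 | 0.469 |
| 0.20 | 0.488 | 0.738 |
| 0.32 (Table 5, whole treatment) | 0.686 | 0.901 |

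**The case against.** The best defence is that Section 3.2 plainly is the definition. It says so, it refers to Section 3.5 only for management, and Section 3.5.1 itself speaks of a DLT definition as something outside Table 6. The DLT entry in the table can be read as a reason for going off treatment, parallel to the unacceptable-toxicity entry for later cycles. A specific exemption would ordinarily override a catch-all row, and modifications are discussed with senior investigators. This makes it likely that Section 3.2 was meant to govern DLT status. It does not settle the orders: even if Section 3.2 governs the count, one text continues the drugs and the other holds or stops them.

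A second defence is Section 6.1.2.1, under which a silent laboratory value may not be an adverse event and so may never enter Table 6. But Section 3.2 says the exempt toxicities are recorded, Section 3.2.2 then refers to them as adverse events, and rash is not a laboratory value. The restriction of Table 6 to treatment-related events does not help either, because the DLT definition has the same restriction.

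Three points for the other side stand. Severe rash was rare in the cited regimens: no grade 3-4 maculopapular rash among 25 patients in Table 5, and one grade 3 case (2%) in Table 5.1. Febrile neutropenia may belong in the ANC row. The probabilities above rest on assumed rates, and those on escalation concern a phase that is over.

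**Conclusion.** The conflict is real and should be corrected. Three items are firm: uninfected grade 4 lymphocytopenia, uninfected grade 3 lymphocytopenia, and grade 3 rash that stops at grade 2. Unresolved febrile neutropenia is softer. Neutropenia and transient electrolyte events conflict in their orders.

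A reader might infer two stronger things that the documents do not support:

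- **That Table 6 makes all uninfected grade 3-4 lymphocytopenia a DLT.** It does so outright only for grade 4. Grade 3 gets the label only if it is still above grade 1 after the hold.
- **That the 20 mg MTD is wrong.** Section 3.3 declares it after escalation closed, no DLT counts are given, and nothing shows that Table 6 was used for counting. For the exempt events Table 6 can only add DLTs, and 20 mg is the top level in Table 2, so over-counting did not push the declared dose down. An effect would need Table 6 to be the governing count, or patients stopped under it to have been replaced. It is possible, not shown.

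The live consequence is in Arm 3: contradictory cycle-1 orders, and possible loss of evaluability for a patient stopped under Table 6. No DLT-based stopping rule applies there, and Section 10.3.1 keeps such a patient in the toxicity population. The chance that at least one of six patients meets the conflict runs from 26 to 90% over assumed rates of 5 to 32%. The true rate is unknown.

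**What to change.** - State that Section 3.2 is the sole definition of a DLT.
- In the cycle-1 block of Table 6, add an exception for the events in Sections 3.2.1-3.2.2 to the grade 3 catch-all row and to the grade 4 row.
- Add a lymphocyte row: continue if uninfected, not a DLT.
- Align the hold instructions for uninfected grade 3 neutropenia and transient electrolyte events with Section 3.2.
- Report Arm 1 DLT counts per dose level on the Section 3.2 definition.

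The cost is protocol wording and a re-tabulation of cycle-1 events already collected. No new patients, visits or procedures are needed.

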3.2.2 Non-Hematologic exceptions

- Transient (< 72 hours) grade 3 hypoalbuminemia, hypokalemia, hypomagnesemia, hyponatremia or hypophosphatemia which responds to medical intervention. Lenalidomide, romidepsin and CC-486 (5-azacitidine) will be continued while the metabolic abnormalities are corrected by intravenous or oral supplementation
- Patients who require short term hospitalization (3 days or less) only for fluid and electrolyte disturbances secondary to anorexia, nausea/vomiting/diarrhea which are common AEs for 5-azacitidine, lenalidomide and romidepsin individually and more so for the combination. This exception does not apply to secondary organ dysfunction resulting from this biochemical derangements or patients that require vasopressor BP support.

- Grade 3 rash that resolves to grade ≤ 2 within 7 days of holding the study drug(s) (See Section 3.5.1 for study drug holding parameters).

Management and dose modifications associated with the above adverse events are outlined in Section 3.5. Occurrence of any DLT-defining toxicity after the first 28 days of treatment will lead to dose modification as specified below; however, it will not be deemed a DLT for purposes of dose escalation.

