3.4.2 Summary of Current Study Design (as of Amendment 12/07/2022)

For the Dose Expansion Cohort 2 Arm 3, treatment will be administered as outpatient for all cycles unless decided otherwise by the principal investigator based on clinical judgment. The standard treatment cycle will be 28 days (4 weeks). Reported adverse events and potential risks are described in Section 14. Appropriate dose modifications are described in Section 3.5. No investigational or commercial agents or therapies other than those described below may be administered during the study therapy period with the intent to treat the patient's malignancy. See **Table 4** below for description of drug regimen.

A cycle may be delayed for the following reasons:

- Scheduling or other administrative reasons (no more than 14 days)
- Administration of COVID-19 vaccination (if the delay would not result in more than 6 weeks treatment-free period)
- Toxicity/dose management as defined below

Table 4: Drug Regimen

Agent	Premedications; Precautions	Dose	Route	Schedule
Lenalidomide	Aspirin for thrombosis prophylaxis	As per dose level***	Oral	Days 1 to 10
Romidepsin	Premedicate with ondansetron or granisetron *	12mg/ m ² in 500 mL NS	IV over 4 hours	Days 1 and 10 (± 2 days)
CC-486 (5-azacitidine)	Premedicate with ondansetron or granisetron **	300mg	Oral	Days 1 to 10
Dexamethasone	No premedication	40mg	Oral	Days 1 and 10 (± 2 days)

* Mandatory for the first cycle; subsequently based on clinical judgement
** Not mandatory, administer based on clinical judgement
*** Doses as appropriate for assigned dose level

For a full detailed product description and administration guidelines, see Section 14. Infusions may be done peripherally or via central venous access device (if present; not required to be placed by the study).

NOTE: Cycles beyond Cycle 1 may not commence until the laboratory criteria in Section 2.1.1.8 are met and non-laboratory treatment-emergent AEs have resolved to grade ≤2 (grade ≤1 if at related to treatment).

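### In cycle 1, Section 3.2.1 treats through isolated grade 3 or 4 lymphocytopenia and does not count it as a DLT, but Table 6 stops or holds treatment and can label it a DLT, and no text says which controls

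*Combined protocol and SAP*

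**What the plan says.** Section 3.2 introduces its list of exceptions with "The following toxicities and conditions will be recorded, however they will not be considered to be DLTs". The first item in 3.2.1 is "Grade 3 or 4 lymphocytopenia without clinical signs of infection grade 2 or above". A sub-bullet then gives a treatment rule with a different condition: lenalidomide, romidepsin and CC-486 "will be continued in the event of asymptomatic grade 3 or 4 lymphocytopenia", unless there are signs of significant infection. It lists those signs: persistent fever, unstable blood pressure, localised complaints or findings, hypoxia, organ dysfunction.

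Section 3.2.2 closes with "Management and dose modifications associated with the above adverse events are outlined in Section 3.5". For Arm 3, Section 3.4.2 says "Appropriate dose modifications are described in Section 3.5".

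Table 6 in 3.5.1 names neutrophils, platelets and haemoglobin among the blood counts. It has no lymphocyte row, so lymphocytopenia falls into the catch-all rows. In cycle 1 these are:

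- Grade 4: the block headed "Grade 4 AEs at any time during cycle 1" has one row, for any AE. Treatment is discontinued and the patient is off treatment as a DLT.
- Grade 3, other AEs: hold for up to 7 days. "If the AE has not improved to" grade 1 or below, the patient is off treatment as a DLT.

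Section 10.3.4 makes a participant evaluable for DLT after completing cycle 1 treatment or having a DLT in it. Anyone who does neither is replaced.

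**The concern.** Two current parts of the plan give opposite instructions for the same event. Under 3.2.1, a patient in cycle 1 with an asymptomatic grade 4 lymphocyte count, treatment-related and without infection, stays on all three drugs and has no DLT. Under Table 6 the same patient stops treatment and has a DLT. Staff following either text are following the protocol.

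For the patient, the stake is loss of a regimen in relapsed or refractory disease because of a laboratory value that the plan elsewhere says to treat through. For the analysis, the stake is that one event can enter the cycle 1 reporting in different ways depending on which text was applied.

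**Working it through.** **The texts side by side, for a related cycle 1 event without infection or symptoms**

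| | Section 3.2.1 | Table 6, cycle 1 |
|---|---|---|
| Grade 4 | Not a DLT; continue | DLT; discontinue |
| Grade 3 | Not a DLT; continue | Hold up to 7 days; off treatment as a DLT if not at grade 1 or below |

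Both texts concern treatment-related events, so relatedness does not separate them. Neither contains an exception for the other.

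**What happens to one grade 4 event**

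1. 3.2.1 applied throughout: no DLT, treatment continues, and the patient is evaluable once cycle 1 is complete.
2. Table 6 applied throughout: DLT, off treatment, evaluable.
3. 3.2.1 for DLT status and Table 6 for treatment: no DLT, off treatment. If this happens before cycle 1 is finished, 10.3.4 makes the patient not evaluable and replaced.

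The third route is open in practice. The calendar in 3.9 schedules a blood count at day 10 (±3), and 3.7 requires assessments before the day 10 romidepsin dose. A count found then can stop that dose.

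**The plan's own figure**

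The plan gives no figure for this event. The only operating figure that depends on what counts as a DLT is the escalation table in 10.2. With P(escalate) = (1−p)³ + 3p(1−p)² × (1−p)³, true DLT rates of 10% to 60% give 0.906, 0.709, 0.494, 0.309, 0.172 and 0.082. These match the stated 0.91, 0.71, 0.49, 0.31, 0.17 and 0.08, so the table is correct.

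To show how much the label could matter, let g be an assumed cycle 1 rate of isolated grade 4 lymphocytopenia, independent of other DLTs, and replace p by q = 1 − (1−p)(1−g). At p = 20%:

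- g = 5%: q = 0.240, P(escalate) = 0.62
- g = 10%: q = 0.280, P(escalate) = 0.54
- g = 18%: q = 0.344, P(escalate) = 0.41

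The value without the extra events is 0.71. Escalation is finished, so this shows only why the definition matters, not what happened.

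**How often Arm 3 could be affected**

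The documents give no cycle 1 rate for this regimen, so 5%, 10% and 9/49 = 18.4% are assumptions. The last comes from Table 5.1 (romidepsin and lenalidomide): 9 patients at grade 4, shown as 18%. The denominator of about 49 is inferred from 9 being 18% and 24 being 49%. Section 10.2 plans 3 to 6 additional patients at the MTD. P(at least one) = 1 − (1−p)ⁿ:

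| p | n = 3 | n = 6 |
|---|---|---|
| 5% | 1 − 0.857 = 0.143 | 1 − 0.735 = 0.265 |
| 10% | 1 − 0.729 = 0.271 | 1 − 0.531 = 0.469 |
| 18.4% | 1 − 0.544 = 0.456 | 1 − 0.296 = 0.704 |

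For grades 3 and 4 together, Table 5 (romidepsin and 5-azacitidine) gives 8/25 = 32%, again over all cycles.

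**The case against.** **3.2.1 is the specific text and should control.** It names lymphocytes and grades, and 3.2 is where DLT is defined. The text before Table 6 itself speaks of a toxicity that "does not meet the definition of a DLT", which points back to 3.2. The laboratory criteria in 2.1.1.8 have no lymphocyte threshold, and 3.4.2 reuses them to gate later cycles. This is good evidence of intent, and it stands for DLT status. It does not settle treatment, because 3.2.2 sends management to Section 3.5. Settling status alone opens the not-evaluable route.

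**An asymptomatic count may not be an AE.** Section 6.1.2.1 records a laboratory abnormality as an AE only under listed conditions. This narrows the overlap. It does not remove it: 3.2 says that these events are recorded, 3.2.2 calls them adverse events, and discontinuation is one of the listed conditions.

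**Table 6 is guidance, discussed with senior investigators.** True, and this would probably prevent some removals. However, 3.11.1 makes toxicities in Section 3.5 that require stopping a criterion for removal from therapy.

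**Little now depends on it.** Much of this stands. No stated expansion decision rule uses a DLT count, and under 10.3.1 all treated patients contribute to the toxicity tables. The removal instruction for Arm 3 remains.

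**The percentages overstate.** This also stands. The 18% covers all cycles. It is not limited to isolated lymphopenia: Table 5.1 shows 9 + 8 + 9 + 4 = 30 grade 4 haematological entries in 18 patients, so events overlap, and a patient who also has grade 4 neutropenia or thrombocytopenia comes off under Table 6 anyway. The MTD given in 1.8 for that pair (romidepsin 14 mg/m² on days 1, 8 and 15; lenalidomide 25 mg on days 1–21) is heavier than the dosing of those two drugs here. That regimen lacks CC-486, which works the other way, so the figures are not strict bounds.

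**Conclusion.** The plan contradicts itself for cycle 1 lymphocytopenia of grade 3 or 4, most sharply at grade 4, and states no order of precedence. The live effect is possible needless removal of Arm 3 patients in cycle 1, together with inconsistent reporting of DLT or evaluability. The number of patients affected cannot be estimated from the documents. The 14% to 46% (3 patients) and 26% to 70% (6 patients) are upper-end illustrations resting on assumed rates. The correction is worth making because it costs almost nothing.

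A reader might infer three stronger things, none of which the documents support:

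- *The 20 mg MTD is unsound.* The documents do not report the cycle 1 events or which text was used to count them, so there is no evidence either way.
- *The contradiction is equally firm in cycles 2–6.* The later catch-all rows also hold, reduce or stop treatment, and the continuation rule has no cycle limit. But that rule sits in the DLT section, so its reach beyond cycle 1 is unclear.
- *Absence of infection of grade 2 or above is enough to continue treatment.* That is the DLT test. Continuation requires the event to be asymptomatic and without the listed signs of significant infection.

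**What to change.** In Table 6, cycle 1, add to the grade 4 any-AE row and the grade 3 other-AE row: *except lymphocyte decrease exempt under 3.2.1*. Add a footnote that keeps the two tests apart: *Lymphocyte decrease, grade 3 or 4: not a DLT when there is no clinical infection of grade 2 or higher; continue the three drugs when asymptomatic, unless a sign of significant infection listed in 3.2.1 is present.*

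Limit the edit to cycle 1 unless the sponsor confirms that the continuation rule was meant for cycles 2–6 as well. Leave the other 3.2.1 events under their present rows. Grade 3 neutropenia has a similar mismatch, with 3.2.1 continuing and Table 6 cycle 1 holding, but that is a separate point.

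In the report, state that DLT counts used 3.2.1. List any patient counted as a DLT, removed or replaced for lymphocytopenia alone.

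The cost is two table cells, one footnote, and one sentence in the report with a short list if anyone was affected. No new data or patients are needed.
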